Radiographic imaging of the dentoalveolar complex has been assessed using conventional periapical radiography, the benchmark for intraoral radiographic imaging for decades. Their known limitations of image magnification, distortion, superimposition and overlap of anatomy always led to unclear and misrepresentation of structures. Although the advent of digital intraoral radiography didn’t improve these limitations, it provided a more active image manipulation than the film-based radiographs and reduced patient exposure substantially. [19, 20]

7 - Objectives and hypothesis:

The objective of this prospective randomized clinical trial is to compare the clinical and radiographic outcomes of MTA and Biodentine as vital pulp therapy materials (pulpotomy) preserving the vitality of traumatized immature anterior permanent teeth.

8-Trial Design:

Randomized clinical trial (RCT), parallel groups with 1:1 allocation ratio, Triple blinded (patient, clinical and radiographic assessor of the results and statistician)

III- Methods:

9-Study settings:

This study will be carried out on patients attending the outpatient clinic in Pediatric Dentistry department, Faculty of Dentistry, Cairo University, Egypt. the procedures will be carried out by [name] Associate Professor of Pediatric Dentistry in Pediatric Dentistry clinic. expected time duration from 2017 to 2018.

10- Eligibility criteria:

Inclusion criteria

- The patient age range 7.5-9 years.
- Noncontributory medical history
- Unilateral/ and or bilateral central incisors tooth with complicated trauma (exposure size $\geq 1\text{mm}$)
- The tooth should give positive response to cold testing
- Clinical diagnosis of reversible pulpitis without periapical rarefaction
- The tooth is restorable, mobility was within normal limits
- No signs of pulpal necrosis including sinus tract or swelling

Exclusion criteria

- Teeth with mature roots
- Signs and symptoms of irreversible pulpitis
- Non-restorable teeth
- Negative response to cold testing, the presence of sinus tract or swelling
- No pulp exposure
- Bleeding could not be controlled after full pulpotomy in 6 minutes

IV- Intervention:

Diagnosis:

1. Full history data will be collected, including personal, medical and previous dental data
2. Clinical examination using mirror and probe to assess the inclusion criteria.
3. Radiographic examination using preoperative digital periapical radiograph to assess the inclusion criteria.

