Secondary outcome	Stage of root development	Standardized periapical	4 stages
	Presence of radiolucency	Standardized periapical	Binary

Primary outcome:

Clinical assessment of the findings in the table will be conducted at follow up intervals (baseline, 6, 12 and 18 months)

Secondary outcome:

Radiographic assessment of stage of root development, and presence of radiolucency will be conducted through digital periapical radiographs by parallel technique using film holders. The assessments will be carried out at follow up intervals (baseline, 6, 12 and 18 months)

13- Participants timeline:

	Study period				
	Enrolment	Allocation	Post allocation		Close out
Time point	For 9 months	0	6 months	12 months	18 months
Enrolment:					
Eligibility screen	✓				
Informed consent	✓				
History taking	✓				
Clinical examination	✓				
Preoperative radiograph	✓				
Allocation		✓			
Interventions:					
Access preparation		✓			
Placement of Biodentine (experimental group)		✓			
Placement of MTA (Control group)		✓			
Final restoration		✓			
Assessment					
Periapical radiograph as baseline reference			✓	✓	✓
Clinical examination to assess pain, swelling, fistula, tooth mobility			✓	✓	✓
Periapical radiograph to assess stage of root development and presence of radiolucency			✓	✓	✓

14- Sample size calculation:

Sample size is calculated based upon the results of Alqaderi et al (2014) [21] who reported clinical success rate (primary outcome) for MTA = 90%. Since no relevant literature reported the clinical success rate of Biodentine in permanent teeth of pediatric patients, the success rate was assumed to be 50%. Using alpha level = 0.05 and β level = 0.20 (80% Power); the minimum estimated sample size will be 20 subjects per group for a total of 40 subjects. To compensate for a drop-out rate of 15%, the number is increased to 23 subjects per group for a total of 46 subjects.

Sample size calculation will be performed using IBM® SPSS® Sample Power® Release 3.0.1.

15- Recruitment:

All patients attending the outpatient clinic in pediatric dentistry department complaining from traumatized immature permanent maxillary central incisors will be screened and enrolled in the study if they meet the eligibility criteria.

16- Allocation:

Sequence generation:

Access cavity in traumatized central incisors will be assigned into experimental or control group using simple randomization 1:1 by the help of the computer software(random.org).

Allocation concealment mechanism:

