All data will be collected, checked, revised, tabulated and entered into the computer. Qualitative data will be presented as frequencies and percentages. Quantitative data will be presented as mean and standard deviation values. Chi-square test and Fisher's Exact test will be used for comparisons regarding qualitative data. Student's t-test will be used to compare between mean age values in the two groups. Friedman's test will be used to study the changes by time within each group. Kaplan-Meier survival curve will be constructed to calculate the mean survival estimates of the two groups. Comparison between survival times will be performed using Log rank test.

The significance level will be set at $P \leq 0.05$. Statistical analysis will be performed with IBM® SPSS® Statistics Version 20 for Windows.

21-Monitoring:

The study data and results will be monitored regularly by the assessor who will have full access to these data.

22- Harms:

No reported adverse effects for both testing pulpotomy agents. Any adverse events appear during the trial will be recorded, documented and treated.

23-Auditing:

Auditing of the study design will be done by the evidence-based committee, Faculty of Dentistry -Cairo University.

V- Ethics and dissemination:

24-Research ethics approval:

This protocol and the template informed consent form will be reviewed by the Ethics Committee of Scientific Research - Faculty of Oral and Dental Medicine - Cairo University.

25-Protocol amendments:

Any modification to the protocol which may have an impact on the conduction of the study, potential benefit of the patient or my affect patient safety including, the changes of study objectives, study design, sample size or significant administrative aspects will require a formal amendment to the protocol.

26-Consent and Assent:

Researcher will discuss the trial with legal guardian of each participating child. They will be able to have an informed discussion with the researcher after explaining the procedure in simple words. Verbal assent will be taken orally from the participating child while written consent will be taken from the legal guardian of each participating child who is willing to participate in the trial. All consent forms will be translated into Arabic.

27-confidentiality:

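### Friedman's test within each arm does not compare the materials, and root stage has no between-arm analysis that uses its order or baseline

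*Combined protocol and SAP*

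**What the plan says.** The objective in Section 7 is a comparison of two materials: "to compare the clinical and radiographic outcomes of MTA and Biodentine as vital pulp therapy materials". Section 12 makes the clinical findings primary and makes root stage (four stages) and radiolucency secondary. All are assessed at baseline, 6, 12 and 18 months; for the primary findings, "Clinical assessment of the findings in the table will be conducted at follow up intervals (baseline, 6, 12 and 18 months").

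Section 20 names these methods for the outcomes:

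- Chi-square and Fisher's: "Exact test will be used for comparisons regarding qualitative data".
- Friedman's: "test will be used to study the changes by time within each group".
- Kaplan-Meier curves for the two groups, and "Comparison between survival times will be performed using Log rank test".

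Student's t-test is reserved for age. One threshold covers everything: "The significance level will be set at" P ≤ 0.05. The section does not say which outcomes Friedman's test covers, whether it is descriptive, or which analysis is primary.

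**The concern.** A Friedman P-value from one arm answers whether that arm changed over time. The trial asks whether the two arms differ. Two within-arm P-values placed side by side do not answer that, and a pair with one below 0.05 and one above invites being read as a difference between materials.

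The within-arm question is also a thin one here. Section 10 requires "No signs of pulpal necrosis including sinus tract or swelling", together with normal mobility and no periapical rarefaction. For those signs, change over time within an arm can only mean that some teeth failed. For root stage it mostly means that children's roots grew.

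The larger stake is root stage itself. Continued root development is a main reason for preserving the pulp in these teeth, and it is the one outcome for which the planned between-arm tools fit poorly.

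**Working it through.** **1. Arm size.** Section 14 states "Using alpha level = 0.05 and β level = 0.20 (80% Power") with success of 90% against 50%. The two-sided pooled formula gives n = [1.96·√(2 × 0.7 × 0.3) + 0.8416·√(0.9 × 0.1 + 0.5 × 0.5)]² / 0.4² = (1.270 + 0.491)² / 0.16 = 19.4, so 20 per arm, as stated. The plan enrols 23 per arm (20 × 1.15). I use 20.

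**2. What each planned method does for root stage.**

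| Method | Compares arms | Uses stage order | Uses the tooth's baseline stage |
|---|---|---|---|
| Friedman, within each group | No | Yes | Yes |
| Chi-square / Fisher | Yes, if applied across arms | No | No |
| Log-rank | Yes | No root-stage event is defined | No |

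No row has all three properties.

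**3. How often identical arms split on a clinical outcome.** Assumptions: 20 teeth per arm, one per child; the sign is absent at baseline; failures persist and are equally likely to start at 6, 12 or 18 months. On binary data the tie-corrected Friedman statistic equals Cochran's Q, referred to chi-square with 3 degrees of freedom.

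- One or two failures in an arm: never significant.
- Three failures: P = 0.029 if all start at the same visit (3 of 27 arrangements, or 1/9); otherwise P = 0.06 to 0.11.
- Four or more failures: always significant (largest P = 0.046).

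So p, the chance that one arm is significant, is P(X ≥ 4) + P(X = 3)/9, with X binomial. The chance that exactly one of two identical arms is significant is 2p(1 − p).

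- 10% failure (the complement of Section 14's 90% for MTA): p = 0.1330 + 0.1901/9 = 0.154; 2 × 0.154 × 0.846 = 0.26.
- 5% failure: p = 0.0159 + 0.0596/9 = 0.0225; 2 × 0.0225 × 0.9775 = 0.044.

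At other assumed rates the split is 0.3% (2% failing), 47% (15%), 48% (20%), 18% (30%) and about 0% (50%). It can never exceed 50%. With 23 per arm, the figure at 10% failure is 34%.

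One tooth can decide it. Four failures of 20 in one arm and three of 20 in the other would usually give one significant and one non-significant Friedman test, while Fisher's test between the arms gives P = 1.0.

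**4. The same for root stage.** The documents give no growth rates, so these are assumptions: start at stage 1 or 2, and a fixed chance of advancing one stage per six months. Simulated splits between identical arms of 20 are 7% at a 2% chance of advancing, 45% at 5%, 27% at 10%, and under 0.5% at 20% or more.

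**5. What a between-arm analysis of change would gain.** In an illustrative simulation (20 per arm, starting stages 1 to 3, assumed advance rates that differ between arms), a rank test on change from baseline to 18 months had power of 75% to 87%. Chi-square on the 18-month stage had 26% to 41%. Advance rates of 10% against 30% per six months give the lower end of both ranges. Type I error was near 5% for both tests.

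**The case against.** The strongest reply is that Section 20 already compares the arms. The log-rank test is a between-arm analysis of outcome across visits. For signs that eligibility makes absent at baseline, status at follow-up is change from baseline, so Fisher's test between arms at a visit compares change directly. This stands. A reader might infer that Friedman's test is the only analysis of the follow-up data, or that no comparison of the materials is planned; the paragraph rules out both.

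Second, the stated purpose of the Friedman tests is to look at change within a group. Nothing says their results will be set against each other or used to judge the materials. This also stands: a misleading contrast is something the plan leaves open, not something it prescribes.

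Third, the 26% depends on its assumptions. The 10% rate is for overall clinical failure, while individual signs are probably rarer. Section IV sends failed teeth to other pulp therapy, so a sign need not persist to 18 months unless failure is carried forward, which is not stated. If each sign shows at one visit only, the split at 10% failure falls to about 6%.

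Fourth, a chi-square test on root stage at 18 months is valid in a randomised trial. That is true. The objection to it is inefficiency, not bias.

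**Conclusion.** The point holds in a limited form. The within-arm Friedman tests do not compare Biodentine with MTA, and Section 20 neither labels them descriptive nor bars their use for that purpose. Clinical failure is nevertheless compared directly by other planned tests. Root stage is the real gap: no planned between-arm method uses the order of its four stages or the tooth's starting stage.

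A reader might infer that identical materials will generally give one significant and one non-significant result. The figures do not support that. The split is about 26% at 10% persistent failure and about 4% at 5%. For root stage it is close to zero if most roots advance: an arm that is significant 98% of the time gives 2 × 0.98 × 0.02 = 4%. All root-stage figures, including the power comparison, rest on growth rates and starting stages that the documents do not give. They show direction, not expected size.

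**What to change.** Amend Section 20 in three respects.

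1. Report within-arm change as counts per visit. If Friedman P-values are kept, label them descriptive and state that they will not be used to judge one material against the other.
2. State that conclusions about the materials rest on the between-arm tests already planned.
3. Add a between-arm ordinal analysis of root stage that uses baseline. This could be a rank test on change in stage at 18 months, or an ordinal model for stage adjusted for baseline stage, with an arm-by-visit term if about 20 teeth per arm will support it.

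The data are already to be collected at the scheduled visits, so no extra visit, radiograph or participant is needed. The cost is a few sentences in Section 20, a little more analysis work, and giving up the within-arm P-values as inference.
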